
Safety Population: All randomized subjects who receive at least 1 dose of study drug.
 
Modified Intent-to-Treat (mITT) Population: All randomized subjects excluding those who subsequently demonstrate a positive test result for other concomitant vaginal or cervical infections at baseline (e.g. C. trachomatis, N. gonorrhoeae) which may interfere with the efficacy assessment for BV or who have a baseline Nugent score<4, received study treatment, and returned for at least one post-baseline visit.
 
Per Protocol (PP) Population: Includes all subjects who qualify for the mITT population and who follow important components of the trial (including subjects who adhere to treatment and follow-up for efficacy within the prescribed timeframe).
 
Subjects in the mITT population who discontinue early from the study and do not have an assessment of clinical cure and bacteriological cure will be included in the mITT population analyses as treatment failures. These subjects without outcomes, but are classified as treatment failures will not be included in the PP analyses.
 
To establish bioequivalence, the 90% confidence interval for the primary endpoint (the difference [test-reference] in proportion of subjects achieving a clinical cure) must be within [-0.20, +0.20], using the PP population.
 
As a parameter for determining adequate study sensitivity, the test product and the reference drug should both be statistically superior to placebo ($p<0.05$, two-sided) for the primary endpoint, using the mITT study population.

Duration of Treatment:
 
Subjects will be treated on Days 1 to 5 with Visit 2 to occur between Days 7 and 14 (inclusive).
 
Test of Cure (Visit 3) will occur between Days 21 and 30 (inclusive) after randomization to assess the primary and secondary endpoints.

Study Duration:
 
Approximately eight months for recruitment and completion of study subject participation.

Compliance:
 
The trial will be carried out in accordance with Good Clinical Practice (GCP) as required by the following: United States (US) Code of Federal Regulations (CFR) applicable to clinical studies (45 CFR Part 46, 21 CFR Parts 50, 54, 56, 312, and 320), ICH E6, and the 2013 revision of the Declaration of Helsinki.

TABLE OF CONTENTS

1	INTRODUCTION AND BACKGROUND	14
2	STUDY OBJECTIVES	15
3	INVESTIGATIONAL PLAN.....	16
3.1	Description of Overall Study Design and Plan.....	16

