2 STUDY OBJECTIVES

Primary Objective:

The primary objective of this study to assess the therapeutic equivalence of an experimental formulation of a metronidazole 0.75% vaginal gel (GDC 229; test product) versus metronidazole 0.75% vaginal gel (Oceanside Pharmaceuticals) in subjects with BV. A vehicle (placebo) arm is included for assay sensitivity.

Secondary Objectives:

The secondary objective of this study is to evaluate the safety and tolerability of an experimental formulation of a metronidazole 0.75% vaginal gel (GDC 229; test product) versus metronidazole 0.75% vaginal gel (Oceanside Pharmaceuticals) and vehicle (placebo) in subjects with BV.

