3.3.1 Inclusion Criteria

Subjects meeting all of the following criteria at Entry Visit (Visit 1) may be considered for study participation:

1. Non-pregnant female aged ≥ 18 years who is in good general health
2. Diagnosis of BV, defined as presence of all of the following:
 - a. Clinical diagnosis of BV (e.g., off-white [milky or gray], thin homogeneous discharge with minimal or absent pruritus and inflammation of the vulva and vagina); AND
 - b. Saline wet mount of vaginal discharge demonstrating the proportion of clue cells to be $\geq 20\%$ of the total epithelial cells; AND
 - c. Vaginal secretion pH > 4.5 , using pH paper that measures from 4.0 to 6.0; AND
 - d. Positive (fish odor) “whiff test” after addition of a drop of 10% potassium hydroxide (KOH) to vaginal discharge.
3. Willing to refrain from vaginal sexual intercourse on Days 1 to 7 (i.e., during treatment and for two post-treatment days) and for 48 hours prior to Visits 2 and 3.
4. Willing to refrain from using any intravaginal product (e.g., spermicide, tampon, douche, feminine deodorant spray, diaphragm, vaginal ring birth control, or condom with spermicide or insertion into the vagina of any drug or non-drug product during treatment), other than study treatment for the duration of the trial.
5. Subjects of childbearing potential who have a negative urine pregnancy test at the Entry Visit (Visit 1) and agree to use an acceptable form of birth control throughout the study. Acceptable forms of birth control include oral contraceptives (the pill), intrauterine devices (IUDs), contraceptive implants under the skin, patches or injections, and condoms without spermicide. Oral or transdermal hormonal contraceptives must be in use for one full cycle (e.g., four to eight weeks) prior to test article application. Injectable or implanted contraceptives (e.g., Depo-Provera, Nexplanon, or hormonal IUD) must be injected/inserted at least seven days prior to test article application. Subjects who are not of childbearing potential, as defined below, must also have a negative urine pregnancy test prior to randomization:
 - a. Postmenopausal for at least one year prior to the Entry Visit (Visit 1) (defined as ≥ 50 years of age and amenorrheic for $>$ one continuous year) or
 - b. Surgically sterile (defined as bilateral tubal ligation, bilateral oophorectomy, or hysterectomy) at least 6 months before first dose or

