3.5.3.4 Adverse Events

3.5.3.4.1 Clinical Trials

There were no deaths or serious adverse events related to drug therapy in clinical trials involving 800 non-pregnant women who received metronidazole vaginal gel.

In a randomized, single-blind clinical trial of 505 non-pregnant women who received metronidazole vaginal gel once or twice a day, 2 patients (one from each regimen) discontinued therapy early due to drug-related adverse events. One patient discontinued drug because of moderate abdominal cramping and loose stools, while the other patient discontinued drug because of mild vaginal burning. These symptoms resolved after discontinuation of drug.

Medical events judged to be related, probably related, or possibly related to administration of metronidazole vaginal gel once or twice a day were reported for 195/505 (39%) patients. The incidence of individual adverse reactions were not significantly different between the two regimens.

Unless percentages are otherwise stipulated, the incidence of individual adverse reactions listed below was less than 1%:

- Reproductive: Vaginal discharge (12%), Symptomatic Candida cervicitis/vaginitis (10%), Vulva/vaginal irritative symptoms (9%), Pelvic discomfort (3%)
- Gastrointestinal: Gastrointestinal discomfort (7%), Nausea and/or vomiting (4%), Unusual taste (2%), Diarrhea/loose stools (1%), Decreased appetite (1%), Abdominal bloating/gas; thirsty, dry mouth
- Neurologic: Headache (5%), Dizziness (2%), Depression
- Dermatologic: Generalized itching or rash
- Other: Unspecified cramping (1%), Fatigue, Darkened urine

In previous clinical trials submitted for approved labeling of Metronidazole Vaginal Gel the following was also reported:

- Laboratory: Increased/decreased white blood cell counts (1.7%)

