4.7.1 Local Site Reactions

Investigator or designee will assess treatment area and rate on a scale of 0 = absent, 1 = mild (slight, barely perceptible), 2 = moderate (distinct presence), and 3 = severe (marked, intense) the following at Visits 2 and 3:

- Erythema
- Petechiae
- Erosion/ulceration
- Edema

The subject will be queried by the Investigator or designee for presence of the following and, if present, the subject will be asked to rate as described above:

- Burning/stinging
- Pain
- Pruritus (itching)

Local site reactions will be collected independently of AEs and will include any reaction that occurs within the treatment area. Local site reactions that require medical intervention (e.g., prescription medication) or extend beyond the treatment area should be documented as an AE.

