2.3 Trial Design

This is a multicenter (with approximately 40 study sites), randomized, double-blind (for both subjects and investigators), vehicle-controlled bioequivalence study with a clinical endpoint. Following completion of the screening procedures, eligible subjects will be randomized in a blinded manner and in a 1:1:1 ratio to one of three treatment arms:

- GDC-229, the test product
- Reference product (metronidazole 0.75% vaginal gel by Oceanside Pharmaceuticals)
- Vehicle (placebo) vaginal gel.

There are three planned study visits as follows:

1. Study entry Visit (Day 1, screening and randomization);

2. Post-Treatment Assessment (Study days 8-15, i.e., 7 to 14 days after randomization), and
3. Test of Cure (Study days 22-31, i.e., 21 to 30 days after randomization).

Though early termination can occur anytime after enrollment, the study generally is up to 31 days in duration for each subject. The study treatment is to be administered intravaginally once daily at bedtime during Study Days 1 to 5.

All procedures and assessments associated with each study visit are shown in the [Appendix 5.1](#) of this SAP. Including a recruitment period of about seven months, the study duration is expected to be approximately eight months.

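### No local site reaction rating is scheduled before or during the five dosing days and no look-back period is stated, so brief untreated irritation is not assured of being recorded

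*Protocol*

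**What the plan says.** - **Objective.** Protocol Section 2 sets out to "evaluate the safety and tolerability of an experimental formulation of a metronidazole 0.75% vaginal gel" against the reference product and vehicle.
- **Dosing and visits.** SAP 2.3 states: "The study treatment is to be administered intravaginally once daily at bedtime during Study Days 1 to 5". It puts Visit 2 at Study Days 8 to 15 and Visit 3 at Study Days 22 to 31. Protocol Table 1 gives Days 7 to 14 and 21 to 30, with Visit 1 as Day 1.
- **The scale.** Under Protocol 4.7.1, repeated in 8.1.1.2, the investigator or designee grades erythema, petechiae, erosion/ulceration and edema. For burning/stinging, pain and pruritus the subject is "queried by the Investigator or designee for presence of the following and, if present, the subject will be asked to rate" on the same scale. The schedule (Protocol Table 3, SAP Appendix 5.1) marks the assessment at Visit 2, Visit 3 and Early Termination, and leaves Visit 1 blank.
- **Look-back.** Protocol 4.7.1, 5.2 and 5.3 state none. Section 5.5 does: an unscheduled visit covers local reactions since the previous visit.
- **Link to adverse events.** Protocol 4.7.1 collects treatment-area reactions separately from AEs and adds: "Local site reactions that require medical intervention (e.g., prescription medication) or extend beyond the treatment area should be documented as an AE". Section 4.7 says that untoward events after the first dose are AEs. Section 8.1.3.1 has staff ask at every visit or contact how the participant has felt since the last one.
- **Entry.** Inclusion criterion 2a describes "thin homogeneous discharge with minimal or absent pruritus and inflammation of the vulva and vagina", so mild itching or inflammation at entry is allowed.
- **Analysis.** SAP 3.8.3 (Table 14.3.5) summarizes the ratings categorically by visit, with no change from baseline.

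**The concern.** Irritation from a vaginal gel is most likely to show while the gel is being used. A subject who follows the schedule has no rating in that period. The rating that comes nearest to it can be read as asking only about the day of the visit. Normally the AE page would catch what such a scale misses, but the separate-collection rule in 4.7.1 weakens that backup for untreated reactions confined to the treatment area.

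The missing baseline adds a second difficulty. Protocol Section 1 lists itching, irritation and burning on urination among the symptoms of BV. These overlap with the items on the scale, and BV is expected to persist more often on vehicle.

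At stake is how informative the local tolerability comparison in Table 14.3.5 can be. The equivalence analysis is not involved.

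**Working it through.** **1. Gap between last dose and rating.** The documents give no figure to reproduce. Inputs are five consecutive daily doses starting the night of Visit 1 (Protocol 3.5.2), the visit windows above, and the SAP 3.4 per-protocol rule, which tolerates a start within 2 days of randomization. Last dose day = start day + 4. Gap = visit day − last dose day.

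| Start day | Last dose day | Visit 2, Protocol Table 1 (Day 7–14) | Visit 2, SAP (Day 8–15) |
|---|---|---|---|
| 1 (on schedule) | 5 | 2 to 9 days | 3 to 10 days |
| 2 | 6 | 1 to 8 days | 2 to 9 days |
| 3 | 7 | 0 to 7 days | 1 to 8 days |

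For Visit 3 with an on-schedule start, the gap is 21 − 5 = 16 to 30 − 5 = 25 days (Table 1), or 22 − 5 = 17 to 31 − 5 = 26 days (SAP). Protocol 5.2 counts 7 to 14 days after randomization, which agrees with the SAP. With on-schedule dosing, the last dose comes before Visit 2 on either numbering.

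**2. Following one case through the rules.** Take moderate burning on nights 2 to 5, confined to the treatment area, untreated and gone by Visit 2.

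| Route | Does it capture the case? |
|---|---|
| Visit 2 rating (4.7.1, 5.2) | Only if the site reads the query as covering the interval; if it reads it as current state, the rating is absent |
| AE page under 4.7 and 8.1.3.1 | Yes, if she mentions it and the site applies the general AE rule |
| AE page under 4.7.1 and 8.1.1.2 | Not directed there: no intervention and no spread |
| Unscheduled visit (5.5) | Yes, if she attends; Appendix 2 tells her to consult the study doctor about significant irritation |
| Early Termination (5.4) | Only if she leaves the study |

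Each route that could capture the case depends on a site's interpretation or on the subject's initiative. Two sites following the protocol could record it differently.

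**3. Baseline and residual BV.** Under the planning assumptions in Protocol 9.1, the uncured share is 1 − 0.36 = 64% on active gel and 1 − 0.20 = 80% on vehicle, a difference of 16 percentage points. Test and reference are assumed to lie within 4 points of each other. Clinical cure at Visit 3 does not itself measure itching or burning, so these figures show only the direction: residual symptoms would tend to raise vehicle ratings relative to both active arms, and could mask irritation from the active gels. Test versus reference is little affected if their cure rates are similar.

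**4. Number of reactions.** The label summary in Protocol 3.5.3.4.1 gives 9% for vulvar or vaginal irritative symptoms. For scale only, 0.09 × 246 ≈ 22 women in an active arm. That trial pooled once- and twice-daily active gel, so the rate need not apply here and gives nothing for vehicle. The share that would be untreated and resolved before Visit 2 is not in the documents, so the number lost cannot be calculated.

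**The case against.** A reader might infer that irritation during dosing is recorded nowhere and that the tolerability objective goes unanswered. The documents do not support that.

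- AE questioning at Visit 2 covers the dosing days. Section 4.7 makes untoward events after the first dose AEs, and 8.1.1.1 says the same of any adverse change from baseline.
- Section 4.7.1 names two cases that must be AEs. It does not expressly forbid recording others, and its scope is any reaction in the treatment area, not only those present on the day.
- The phrase about presence decides whether a severity grade is requested; it does not fix a recall period. The two CRF questions in SAP 3.8.3 are in the past tense, which is compatible with interval reporting.
- Unscheduled and Early Termination visits also record reactions, and Appendix 2 asks subjects to tell staff about side effects.
- Baseline is not wholly absent. The gynecological examination records vulva, vaginal wall and cervix as normal or abnormal, with change from baseline (SAP 3.8.6, Table 14.3.8). Randomization also protects the arms against imbalance at entry.

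Most of this stands and limits the point to transient, untreated irritation. It does not remove it. A recall period that can be read two ways will be applied two ways, and 5.5 shows that look-back wording was available. Sections 4.7 and 4.7.1 still pull in different directions. The normal/abnormal examination has no symptom item and no grade. Randomization balances symptoms at entry, but not their resolution under different treatments.

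**Conclusion.** The point holds as a limit on sensitivity. No graded local reaction rating is scheduled before or during dosing. The first scheduled one comes 2 to 9 days (Protocol Table 1) or 3 to 10 days (SAP) after an on-schedule last dose, less with a late start, and has no stated look-back. Untreated irritation that resolves before Visit 2 is not assured of a place in either the reaction or the AE data, so the tolerability objective is answered with low sensitivity to it. The lack of a baseline score mainly weakens comparisons with vehicle.

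Two stronger conclusions should not be drawn. The plan would not report good tolerability whatever happened: treated or spreading reactions, AEs by severity and relatedness, discontinuations and reactions still present at Visit 2 would all show. Nor are 22 reactions per arm lost; that figure illustrates a rate from another setting. The verdict assumes that no diary, scheduled contact during dosing or CRF instruction outside the protocol and SAP supplies the missing look-back; these documents describe none. The primary equivalence conclusion is unaffected. The change is worth making because it is cheap and serves a stated objective.

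**What to change.** 1. At Visit 2, have the subject rate the worst burning/stinging, pain and pruritus since the first dose as well as the current state. At Visit 3, ask for the worst since Visit 2.
2. Score all seven items before dosing at Visit 1, at the pelvic examination already planned.
3. In Table 14.3.5, summarize by arm the worst rating and the treatment-emergent reactions (change from baseline).
4. Reconcile Protocol 4.7 with 4.7.1 and 8.1.1.2, so that every site records an untreated, localized reaction in the same place.
5. While that text is open, align the scale and rater. The protocol grades 0 to 3 and has the investigator or designee rate four signs; SAP 3.8.3 grades 1 to 4 and has subjects rate all seven items. Align the Visit 2 day numbering as well.

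The cost is an extra rating field at Visits 2 and 3, one more use of an existing CRF page at Visit 1, and additional table work. No new visit or procedure is needed. The drawback is that recall over up to two weeks is imperfect, though a stated window is better than an unspecified one.

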4.8 Clinical Laboratory Evaluations

4.8.1 Urine Drug Screening

At the Entry Visit (Visit 1), urine drug screening will be completed.

4.8.2 Pregnancy Testing

Pregnancy testing via urine hCG testing (serum hCG testing will be done only if deemed necessary by the PI) will be performed for each subject, regardless of childbearing potential, at each visit. Additional pregnancy testing may also be performed if there is any suspicion or clinical concern that a woman might be pregnant at any time during the study.

4.8.3 Screening for Sexually Transmitted Infections

At the Entry Visit (Visit 1) pelvic examination, a sample will be collected for assessment of sexually transmitted infections (STI) for *Chlamydia trachomatis*, *Neisseria gonorrhoeae*.

4.8.4 Microbiological Sample

A wet smear microbiological sample will be collected at each visit in order to determine if Amsel's criteria are met/or resolved. Evidence of any vulvovaginitis other than BV. (e.g., vulvovaginal candidiasis, *Trichomonas vaginalis*, *Chlamydia trachomatis*, *Neisseria gonorrhoeae*, active Herpes simplex, or active HPV will also be ruled out in order to ensure study eligibility. In addition, a specimen for Gram stain will be collected at Visits 1 and 3. Details for collection, preparation, and evaluation of microbiological samples by the central lab will be provided in the study laboratory manual.

5 SCHEDULE OF ASSESSMENTS AND STUDY VISIT PROCEDURES

The study will include three visits:

- Entry Visit (Visit 1)
- Post-Treatment Assessment (Visit 2)
- Test of Cure (Visit 3)

Refer to [Table 3, Schedule of Assessments](#).

5.1 Entry Visit (Visit 1)

During the screening portion of the Entry Visit (Visit 1), the following should be completed:

- Obtain written informed consent.
- Perform urine pregnancy test.
- Review and confirm inclusion and exclusion criteria.
- Obtain demographic data.
- Collect medical and gynecological history, including sexual history, information on the subject's menstrual cycle, and history of STIs.
- Obtain vital signs after sitting for 5 – 10 minutes ([Section 4.5](#)).
- Record height and weight.
- Record current medications and prior medications taken within three months prior to the start of screening, in addition to the indication for the medication and reasons for discontinuing medication.
- Perform complete physical and pelvic examination including a vaginal wall inspection (i.e., a naked eye inspection) as well as an examination of the cervix.
- Perform urine drug screening.
- Collect Chlamydia and gonorrhea swab samples for central laboratory analysis.
- Collect a swab sample for central laboratory Nugent's analysis for BV via Gram stain.
- Screen for presence of BV by assessing the subject for presence of the four Amsel's criteria. (Note: The four Amsel's criteria are the only BV diagnostic criteria on which the decision to randomize is made; Nugent's result is not used for randomization decisions). If the results of the Amsel's screening tests are positive and the subject is eligible according to all other inclusion/exclusion criteria, the subject can be randomized to treatment:
 - Clinical diagnosis of BV (e.g., thin, homogeneous off-white [milky or grayish] vaginal discharge associated with minimal or absent pruritus inflammation); AND
 - Saline wet mount of vaginal discharge demonstrating the proportion of clue cells to be $\geq 20\%$ of the total epithelial cells; AND
 - Vaginal secretion pH > 4.5 ; AND

- Positive “whiff test” after addition of a drop of 10% KOH to vaginal discharge.
- Assess the saline wet mount for evidence of any vulvovaginitis other than BV. (e.g., vulvovaginal candidiasis, *Trichomonas vaginalis*, *Chlamydia trachomatis*, *Neisseria gonorrhoeae*, active herpes simplex, or active HPV) per laboratory manual.
- An overall determination of the subject’s eligibility will be made based on the results of the assessments noted above as well as all inclusion and exclusion criteria (see [Section 3.3](#)).
- Dispense study medication, explain appropriate application to subjects, and give the subject a copy of the Subject Dosing Instructions for Study Medication ([Appendix 2](#)).
- Schedule the subject for Visit 2 and Visit 3 and add the visit dates to page 2 of the Subject Dosing Instructions for Study Medication. Note: The subject should not be menstruating during the five days of study medication administration or be scheduled for Study Visits 2 or 3 when menstruating in order for assessments to be accurate.

5.2 Post-Treatment Assessment (Visit 2)

Visit 2 will occur 7 to 14 days after randomization. During this visit, the following procedures will be performed:

- Obtain vital signs after sitting for 5 – 10 minutes ([Section 4.5](#)).
- Perform urine pregnancy test.
- Perform pelvic examination including vaginal wall inspection (a naked eye inspection), examination of the cervix, and Investigator’s assessment of local site reactions.
- Record subject-assessed local site reactions (e.g., itching, burning/stinging, localized pain).
- Perform clinical test of response by assessing the subject for presence of these three of the Amsel’s criteria:
 - Resolution of the abnormal vaginal discharge characteristic of BV to a normal physiological discharge; AND
 - Negative “whiff test” after addition of a drop of 10% KOH to vaginal discharge; AND
 - Presence of clue cells at <20% of the total epithelial cells on microscopic examination of the saline wet mount.
- Determine if vaginal pH is <4.7, which is part of the assessment of therapeutic cure (defined as clinical cure, vaginal pH <4.7 and bacteriological cure).
- Record concomitant medications taken since the prior visit along with the indications for the medications.
- Study medication remaining in the tube will be returned by subjects, including unused applicators. Verify that the subject inserted the medication according to instructions and for five consecutive days.
- Assess and record AEs.

- Confirm the date of the subject's Visit 3 will still likely occur on a day that the subject is not expecting menstruation. Note: The subject should not be menstruating during the five days of study medication administration or be scheduled for Study Visits 2 or 3 when menstruating in order for assessments to be accurate.

